15.5 Adverse Event Reporting Requirements

The information to be reported in AEs will be assessed by and assigned severity using the National Cancer Institute Common Terminology Criteria for Adverse Events (NCI CTCAE), Version 4.03. The NCI CTCAE provides descriptive terminology and a grading scale for each adverse event listed. A copy of the NCI CTCAE v4.03 can be downloaded from the CTEP home page (<http://evs.nci.nih.gov/ftp1/CTCAE/About.html>).

Information to be reported in the description of each adverse event may be included, but is not limited to:

1. Clinical Diagnosis of the event as determined by NCI CTCAE, Version 4.03 descriptive terminology. If no clinical diagnosis can be identified, each sign/symptom should be reported as a separate independent event.
2. Date of onset of the AE (start date).
3. Date of resolution of the AE (end date).
4. Severity of the event determined by NCI CTCAE, Version 4.0 grading scale.
5. Relationship of the AE to study therapy. Categorized as follows:

Definite	The adverse event is clearly related to the investigational agent(s)
Probable	The adverse event is likely related to the investigational agent(s)
Possible	The adverse event may be related to the investigational agent(s)
Unlikely	The adverse event is doubtfully related to the investigational agent(s)
Unrelated	The adverse event is clearly not related to the investigational agent(s)

6. Whether or not the AE is Serious or Not Serious as defined in Section 15.3 Serious Adverse Events.
7. Whether the AE is Suspected and/or Unexpected.

Suspected	Any AE for which there is a reasonable possibility that the drug caused the AE. For the purposes of expedited safety reporting, ‘reasonable possibility’ means there is evidence to suggest a causal relationship between the drug and the AE.
Unexpected	Any AE for which the nature or severity of the event is not consistent with the applicable product information, e.g., the Investigator’s Brochure or Package Insert.

8. Action taken as a result of the AE.
9. Outcome.

15.6 Expedited Adverse Event Reporting Requirements

All AEs, regardless if serious or not, will be described in the source documents, reported on the applicable AE page of the CRFs, and entered into *Velos*. However, certain adverse events must also be reported in an expedited manner for more timely monitoring of patient safety and care. Appendix A provides information about these expedited reporting requirements.

16.0 STATISTICAL CONSIDERATIONS

16.1 Objectives and Endpoints

This is a single-arm phase II trial of Pembrolizumab (Keytruda®) in patients with advanced, unresectable hepatocellular carcinoma. The primary objective is to assess its therapeutic efficacy in patients with unresectable hepatocellular carcinoma (HCC). The

primary endpoint is disease-control rate (DCR) defined as the proportion of patients achieving a best overall response of either a CR, PR or SD (that is maintained for at least 8 weeks).

Secondary endpoints include progression-free survival (PFS), overall survival (OS), objective response rate (ORR), duration of response (DOR), and toxicity profile of Pembrolizumab. We will also evaluate the expression levels of PD-L1 in tumor tissue, as well as serum titers of hepatitis B or C in patients with hepatitis B or C, respectively, for whom specimens are available.

16.2 Study Design and Sample Size Justification

The primary endpoint for this single arm phase II trial is disease control rate (CR, PR, or SD). The rationale for using disease control rate (DCR) as the primary endpoint is derived from the clinical experience with Sorafenib (SHARP trial 2008), which was approved as the first and only therapeutic agent definitively proven to prolong survival in patients with advanced HCC. The disease control rate of Sorafenib was 43% in the SHARP trial [7]. We hypothesize that Pembrolizumab will achieve a similar or higher disease control rate. We set a null hypothesis rate of 18% disease control, since standard chemotherapy regimens generally result in a DCR of 15-20%.

We propose study size based on the Simon 2-stage MiniMax design [39] with a one-sided significance level of 5% and 90% power. Assuming that Pembrolizumab therapy will not be of further interest if DCR were no better than 18% (null hypothesis) while a rate of 43% would merit further investigation, the Simon MiniMax design requires at most 28 patients: 14 patients to be enrolled in the first stage and possibly an additional 14 in the second stage. If no more than 2 of the 14 patients in stage 1 achieve CR/PR/SD, the trial will stop and Pembrolizumab will be considered ineffective. If 3 or more of the stage 1 patients achieve CR/PR/SD, our study will continue to a second stage and enroll an additional 14 patients for a total of 28. If 9 or more out of 28 study patients achieve CR/PR/SD, we will report an observed DCR of at least 32% and conclude that the true DCR significantly exceeds a null rate of 18%. With this design, the chance of early stopping at the end of stage 1 is 53% if the null hypothesis of 18% DCR is true, whereas there is a very small chance, 2%, of early termination if the true DCR is 43%.

16.3 Analysis Set

Patients who are study eligible and receive at least one dose of Pembrolizumab will be considered evaluable for efficacy and toxicity, and will comprise the main analysis set.

Any patient who is enrolled on study but does not receive study treatment will be excluded from all analyses. Any patient who receives study treatment but is later found to be ineligible (e.g. protocol violation) will be withdrawn from study but will be followed for response, toxicity, and survival. The experience of such patients will be characterized separately from that of evaluable patients. Reasons for all exclusions will be characterized, such as eligibility subsequently not confirmed, or failure to receive treatment.

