3.0 ENDPOINTS

3.1 Primary endpoints

- Disease control rate (DCR) will be calculated per RECIST 1.1, as the proportion of patients with best overall response of complete response (CR), partial response (PR) or stable disease (SD) that is maintained for at least 8 weeks.
- Treatment-related adverse events (AEs) including serious adverse events (SAEs). AEs will be assessed by and assigned severity using the National Cancer Institute Common Terminology Criteria for Adverse Events (NCI CTCAE), Version 4.03.

3.1.1 Evaluable:

- Evaluable for DCR: Eligible subjects who receive at least one dose of pembrolizumab, have measurable disease at baseline, and have at least one post-baseline disease response assessment.
- Evaluable for Safety: Eligible subjects who receive at least one dose of pembrolizumab.

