17.0 DATA REPORTING

Data must be submitted according to the protocol requirements for all patients registered. Patients for whom documentation is inadequate to determine eligibility will generally be deemed ineligible.

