17.1 Data and Safety Monitoring

The Sylvester Comprehensive Cancer Center (SCCC) Data and Safety Monitoring Committee (DSMC) will monitor this clinical trial according to the Cancer Center's DSM Plan. In its oversight capacity, the DSMC bears responsibility for suspending or terminating this study. DSMC oversight of the conduct of this trial includes ongoing review of accrual and adverse event (AE) data, and periodic review of the study therapy. The guidelines appearing in this section are offered for DSMC consideration in assessing AEs and response to study treatment. In addition, the DSMC will review reports from all audits, site visits, or study reviews pertaining to this clinical trial and take appropriate action. The SCCC DSM Plan to which this study is subject can also be found at www.sylvester.org.

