17.2.2 Safety: Early Stopping Due to Excessive Toxicity

We propose the following guidelines for the DSMC in its review of accumulating data on toxicity. The proposed guidelines were developed using Bayesian methods, which can be applied at any stage of enrollment without advance specification of the number of interim analyses to be performed, or the number of patients evaluable for toxicity, at the time such assessments are made [43-44].

Under the Bayesian method, we assign a prior probability (level of belief at the start of the trial) to a range of possible values for the true toxicity rate. As data on treated patients become available, each of these probability distributions is revised

and the resulting posterior probability becomes the basis for recommending either early termination or continuation of the study. Specific stopping guidelines and details on the prior distribution assumptions, and the resulting posterior probabilities are presented below.

For purposes of safety monitoring, we define an unacceptable toxicity to be any treatment-related (i.e., possible, probable, or definite) grade 3 or higher toxicity excepting nausea, reversible elevation of liver function tests and reversible myelosuppression. Prolonged (defined as ≥ 12 weeks,) grade 3 or higher elevation of liver function tests or myelosuppression will be considered unacceptable. Patients with hepatitis may take longer to recover their counts but it is considered justifiable given their poor prognosis. Early stopping (suspension and possibly termination) will be considered if there is evidence that the proportion of patients experiencing unacceptable toxicity exceeds 20%.

Specifically, we suggest as a guideline for early termination, a posterior probability of 90% or higher that the rate of unacceptable toxicity exceeds 20%. The table below shows specific instances where this guideline is met, thus suggesting early termination due to evidence of excessive toxicity.

For example, if 8 evaluable patients have been assessed for toxicity, the second row of the above table indicates that early stopping should be considered if 4 (or more) of these patients have experienced unacceptable toxicity. Note that 4 of 8 patients with unacceptable toxicity is an observed toxicity rate of 50%.

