19.5 Recording and Processing of Data

If using hard copies of CRF's, study center personnel will complete individual CRF's in black ink. All corrections to entered data will be made by drawing a single line through

the information to be corrected without obscuring it. All corrections will be initialed, dated and explained, if necessary. The use of “white-out” or obscuring correction tape will be prohibited. A CRF is required for every patient who received any amount of study treatment. The investigator will ensure that the CRF’s are accurate, complete, legible and timely. Separate source records are required to support all CRF entries except those for which use of the CRF as source document is clearly allowed per note in the investigator study file.

Data must be submitted according to the protocol requirements for ALL patients registered. Patients for whom documentation is inadequate to determine eligibility will generally be deemed ineligible.

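### The main safety set leaves out dosed patients later found ineligible, and the denominator of the advisory toxicity guideline in 17.2.2 is not clearly stated

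*Combined protocol and SAP*

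**What the plan says.** **Safety set.** Section 16.3 states: "Patients who are study eligible and receive at least one dose of Pembrolizumab will be considered evaluable for efficacy and toxicity". These patients form the main analysis set. Section 3.1.1 agrees: "Evaluable for Safety: Eligible subjects who receive at least one dose of pembrolizumab".

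**Dosed, then found ineligible.** Under 16.3 a treated patient who "is later found to be ineligible (e.g. protocol violation) will be withdrawn from study but will be followed for response, toxicity, and survival" stays under observation, but "The experience of such patients will be characterized separately from that of evaluable patients". Section 16.3 also mentions eligibility that is subsequently not confirmed as a reason for exclusion. Section 17.0 adds: "Patients for whom documentation is inadequate to determine eligibility will generally be deemed ineligible".

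**Data capture.** Section 19.5: "A CRF is required for every patient who received any amount of study treatment".

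**Toxicity guideline.** Section 17.2.2 suggests early termination when the posterior probability that the unacceptable-toxicity rate exceeds 20% is 90% or higher. Its worked example begins "if 8 evaluable patients have been assessed for toxicity". The method paragraph of the same section speaks instead of data on treated patients, and the table column counts patients evaluated. Section 17.1 fixes the status of the rule: "The guidelines appearing in this section are offered for DSMC consideration in assessing AEs and response to study treatment".

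**Adverse event windows.** Footnote J of the calendar in 12.6 continues AE/SAE collection for at least 90 days after the end-of-treatment visit. Section 15.4 covers all AEs up to 30 days after the last dose. Sections 12.2 and Appendix A end the 90-day SAE window early if new anti-cancer therapy starts; 12.4 does not.

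**The concern.** An eligibility restriction can be defended for an efficacy rate. For toxicity the relevant fact is that the patient received the drug. Under 16.3 and 3.1.1 a patient can leave the headline toxicity tables after the toxicity is known, for a reason such as incomplete eligibility documentation that has nothing to do with exposure.

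Section 3.1 makes treatment-related AEs a primary endpoint (16.1 lists toxicity as secondary; the point holds either way). The study is single-arm and open-label with 28 evaluable patients planned, so each patient carries 1/28 = 3.6 percentage points and no control arm is subject to the same selection.

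The second stake is the number put before the DSMC. If the 17.2.2 count follows the defined meaning of 'evaluable', an eligibility ruling can change whether the 90% guideline reads as met.

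**Working it through.** **Inputs.** Prior Beta(0.4, 1.6), threshold rate 20%, cut-off 90%, and limits printed for totals 4 to 27 (all 17.2.2).

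**Formula.** With x unacceptable toxicities in n patients, the posterior is Beta(0.4 + x, 1.6 + n − x). The guideline is met when P(rate > 0.20) ≥ 0.90.

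**Reproducing the plan.** The prior probability above 20% is 0.361 (plan: 36%). The smallest x reaching 0.90 matches the printed limit at 23 of the 24 totals from 4 to 27. The exception is 10, where the printed 4/10 gives 0.895 and the computed limit is 5. None of the worked examples below uses that cell.

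**One dosed patient excluded, near a limit.**

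| Excluded patient | Before | After | Advisory signal |
|---|---|---|---|
| had unacceptable toxicity | 4/8: 0.950 | 3/7: 0.873 | lost |
| had none | 3/7: 0.873 | 3/6: 0.914 | gained |
| had none | 5/14: 0.886 | 5/13: 0.913 | gained |

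**Which direction, and where.** If the limit is the same at n and n − 1, removing an affected patient from a count at the limit loses the signal. If the limit at n − 1 is one lower, removing an unaffected patient from a count one below the limit gains it. With the computed limits, totals 5 to 27 split into 17 where a signal can only be lost and 6 (7, 10, 14, 18, 22, 26) where it can only be gained.

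**Conditional size.** Assume exactly one dosed patient is excluded, at random with respect to toxicity, and X ~ Bin(n, p) with p = 20%, 30%, 40%. The chance that a single look reads differently is:

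- n = 8, lost: P(X=4) × 4/8 = 2.3%, 6.8%, 11.6%
- n = 14, gained: P(X=5) × 9/14 = 5.5%, 12.6%, 13.3%
- n = 20, lost: P(X=7) × 7/20 = 1.9%, 5.7%, 5.8%
- n = 27, lost: P(X=9) × 9/27 = 1.4%, 5.0%, 4.2%

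Averaged over totals 5 to 27, lost against gained is 1.6% against 1.4% at p = 20%, 4.7% against 3.2% at 30%, and 5.9% against 3.1% at 40%.

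**Headline rate.** Assume 6 events in 28 eligible patients (21.4%). With one excluded patient the all-dosed rate is 6/29 = 20.7% to 7/29 = 24.1%. With three it is 6/31 = 19.4% to 9/31 = 29.0%. The ends are none or all of the excluded patients having an event. The counts 6, one and three are assumptions, not document figures.

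**Limits beyond the printed table.** The same prior and rule give 9 at 28–29 (0.920, 0.903), 10 at 30–33 (0.946 at 30, 0.904 at 33) and 11 at 34–35 (0.945, 0.933).

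**Windows, side by side.** Footnote J and 15.4 differ in length (at least 90 against 30 days) and in starting point (end-of-treatment visit against last dose). For SAEs, 12.2, 12.4 and Appendix A agree on 90 days. Appendix A handles non-serious events of clinical interest like SAEs, and 8.4.1.1 also separates SAEs and these events after day 30. That leaves the conflict on non-serious AEs that are not events of clinical interest. Section 16.5 tabulates toxicities by grade without a lower limit, so for those tables the gap covers any grade; for the 17.2.2 count it covers only events meeting the unacceptable-toxicity definition.

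**The case against.** The strongest reply is that little is hidden. The exclusion is pre-specified, the patients are followed for toxicity and described separately with reasons, and 19.5 requires a CRF for each, so a reader can add the two groups. This stands: the defect is in the headline rate, not in data capture.

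Second, Section 6.0 requires eligibility review with a signed checklist and source documents before entry, so late rulings may be rare. This also stands. A reader might infer from the protocol-violation example in 16.3 that any breach, even one unrelated to an entry criterion, removes a patient. The text does not support that: the same section speaks of being found ineligible and of eligibility not being confirmed.

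Third, a reader might infer that the stopping count definitely excludes these patients. It may not, because 17.2.2 also speaks of treated patients. The supported finding is an unstated denominator.

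Fourth, a reader might infer that exclusion always hides toxicity. It can also create a signal, and under random exclusion the two directions are nearly balanced at a true rate of 20%, with a modest net loss at 30% and 40%.

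Fifth, the assumed shifts in the headline rate lie inside sampling error: the exact 95% interval for 6/28 is 8.3% to 41.0%. True, but imprecision is no reason to leave exposed patients out.

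On the windows, footnote J and 12.4 both refer to Section 15.0 and Appendix A, which softens the conflict without removing it.

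**Conclusion.** The point holds for the safety set: 3.1.1 and 16.3 keep dosed patients who are later found ineligible out of the main toxicity rates. For 17.2.2 it holds conditionally. The denominator is ambiguous, and if 'evaluable' carries its defined meaning, one exclusion near a limit can lose or gain the advisory signal.

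The documents give no rate of post-dose ineligibility, so the frequency cannot be sized; every percentage above is conditional on an exclusion happening and on the stated assumptions. The documents do not support reading this as a failed or bypassed stopping rule: the guideline is advisory and the DSMC reviews AE data on an ongoing basis. The change is worth making because it costs little and removes a choice that could be made after toxicity is known.

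The window conflict is real, minor and separate. Its size is unknown because no rate of such events after day 30 is given.

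**What to change.** - In 3.1.1 and 16.3, define the safety set as all patients who receive at least one dose, regardless of eligibility. Add an eligible-only toxicity table as a sensitivity analysis.
- In 17.2.2, state that numerator and denominator both use that set, in the method text, the example and the table.
- Extend the printed limits: 9 at 28–29, 10 at 30–33, 11 at 34–35. The table already stops one short of the 28 evaluable patients planned. The 35 in 16.4 is a ceiling on enrollment, part of it meant for screen failures according to the revision history, so 35 dosed patients is an upper bound.
- Separately, reconcile 12.2, 12.4, 15.4, footnote J and Appendix A on window length, starting point and the effect of new anti-cancer therapy, and state which events feed 17.2.2.

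**Cost.** Wording and a few table rows for the safety set, since toxicity follow-up and a CRF are already required. The downside is that truly ineligible patients, for example with worse liver function, enter the headline rate, which may be slightly higher; the eligible-only table addresses this. The window change may add some AE data entry, depending on how the passages are reconciled.

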16.4 Patient Enrollment and Study Duration

We plan to enroll up to 35 patients, to ensure that we have a minimum of 28 patients who are evaluable for the primary efficacy endpoint for this study, disease control rate (DCR). We expect to enroll 10-12 patients per year based on our institution's enrollment capacity.

Accrual will be suspended after 14 evaluable patients (stage 1) in order to assess DCR in accordance with the two-stage design of this trial.

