7.0 STUDY DESIGN

The study will be an open-label, single-institution, non-randomized, single-arm, Phase II study of pembrolizumab therapy in patients with advanced HCC. Patients will be treated in three-week cycles, with intravenous (IV) administration of pembrolizumab on day 1 of each 3-week cycle. Trial therapy will last until withdrawal of consent, disease progression and/or unacceptable toxicity, whichever occurs first.

Correlative studies investigating PD-L-1 expression in tumor tissue will be assessed with clinical outcome. Peripheral blood will also be drawn to perform immunologic markers and hepatitis B or C viral titers. This is to determine if viral titers change with treatment. These studies are included for all patients who consent to the correlative studies (See Appendix F). There is an additional consent for the correlative studies.

Up to 28 evaluable patients will be enrolled at Sylvester Comprehensive Cancer Center (SCCC). We expect to enroll 10-12 patients per year based on our institution's enrollment capacity. Expected time to complete total accrual is approximately 1.5 years. Expected time to study completion is 3 years from date open to enrollment to allow for survival data. An interim analysis is planned after 14 evaluable patients are assessed for DCR to determine whether to continue with an additional 14 more.

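### The plan makes 28 evaluable patients a maximum in some sections and a minimum in Section 16.4, and its only success rule is undefined for 29 or more

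*Combined protocol and SAP*

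**What the plan says.** The sections of the combined protocol and SAP that bear on the number of evaluable patients are these.

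- **Section 16.2** sets the design at a "one-sided significance level of 5% and 90% power". On the null: "We set a null hypothesis rate of 18% disease control". On the alternative: "a rate of 43% would merit further investigation". It adds that "the Simon MiniMax design requires at most 28 patients", split 14 and 14, with a stop if 2 or fewer of the first 14 have disease control. Success is worded as "If 9 or more out of 28 study patients achieve CR/PR/SD", and the same sentence ties this to an observed DCR of at least 32%.
- **Section 7.0**: "Up to 28 evaluable patients will be enrolled at Sylvester Comprehensive Cancer Center".
- **Section 17.2.3** describes stage 2 as 14 more patients, bringing the evaluable total to 28.
- **Section 16.4**: "We plan to enroll up to 35 patients, to ensure that we have a minimum of 28 patients who are evaluable" for DCR. It suspends accrual after the 14 evaluable patients of stage 1. No similar pause is stated near the end of stage 2.
- **Section 3.1.1** requires eligibility, one dose, measurable disease at baseline and at least one post-baseline assessment for a patient to be evaluable for DCR.
- **Section 16.3** requires only eligibility and one dose for efficacy, and puts all such patients in the main analysis set with no cap.

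No section gives a cut-off for any total other than 28, and none says which 28 patients enter the decision if more qualify.

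**The concern.** The cut-off of 9 was derived for a total of exactly 28, and at that total the design uses almost all of its 5%. Once 28 becomes a minimum, the final total may differ from the one for which the rule was built, and the plan does not say what happens then.

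The criterion is expressed both as a count (9) and as a rate (at least 32%). The two agree at 28 but can part company at 29. In an open-label, single-arm trial, the choice between them could be made after the responses are known. What is at stake is the trial's only formal efficacy claim, that the DCR significantly exceeds 18%.

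**Working it through.** **Inputs.** From Section 16.2: p0 = 0.18, p1 = 0.43, n1 = 14, stop if at most 2, total 28, success if at least 9. From Sections 16.4 and 7.0: 10 to 12 patients per year. From Section 7.0: accrual in about 1.5 years. From Section 12.0: imaging every 9 weeks (±9 days).

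**Formula.** For total n and cut-off c, with the stage 1 rule unchanged:

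P(success | p) = Σ over x = 3,…,14 of P[Bin(14, p) = x] × P[Bin(n − 14, p) ≥ c − x]

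**Step 1: the plan's own design.** With n = 28 and c = 9, type I error is 0.0495 at p = 0.18 and power is 0.9048 at p = 0.43. Early stopping has probability 0.5256 under the null and 0.0242 under the alternative, matching the stated 53% and 2%. A search over two-stage designs meeting 5% and 90% gives 28 as the smallest maximum total. Among designs of that size, this one has the lowest expected sample size under the null (20.6). Section 16.2 is therefore correct as a Simon minimax design.

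**Step 2: totals above 28, under each reading.** The rate-based cut-off is the smallest whole number c with c/n at least 9/28. For example, 30 × 9/28 = 9.64, so c = 10.

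| n evaluable | type I error, count of 9 kept | rate-based cut-off | type I error, rate kept |
|---|---|---|---|
| 28 | 0.0495 | 9 | 0.0495 |
| 29 | 0.0599 | 10 | 0.0249 |
| 30 | 0.0714 | 10 | 0.0312 |
| 31 | 0.0839 | 10 | 0.0384 |
| 32 | 0.0972 | 11 | 0.0195 |
| 33 | 0.1114 | 11 | 0.0244 |
| 34 | 0.1261 | 11 | 0.0300 |
| 35 | 0.1414 | 12 | 0.0153 |

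Nine of 30 is 30%: a success by count, a failure by rate.

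**Step 3: how large an overrun is plausible.** Under Section 3.1.1, evaluability is settled only at the first post-baseline assessment, scheduled about 9 weeks after the start. If accrual continues while those scans are awaited, 10 to 12 per year gives 10 × 9/52 = 1.7 to 12 × 9/52 = 2.1 further patients. Accruing 28 in 1.5 years (78 weeks) gives 28 × 9/78 = 3.2. A total of 29 to 31 is therefore plausible without departing from Section 16.4.

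**Step 4: dosed patients without a scan.** Under Section 16.3 these patients enter the analysis set. If they count as failures, they add no disease controls. The chance of reaching 9 is then still that of the 28 scanned patients, so they do not raise the error rate.

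**Step 5: candidate repairs.**

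| Rule | Type I error | Power at 43% |
|---|---|---|
| First 28 evaluable, at least 9 | 0.0495 | 0.905 |
| n = 29, at least 10 | 0.0249 | 0.862 |
| n = 30, at least 10 | 0.0312 | 0.888 |
| n = 31, at least 10 | 0.0384 | 0.909 |
| n = 32, at least 10 | 0.0466 | 0.926 |
| n = 33, at least 11 | 0.0244 | 0.894 |
| n = 34, at least 11 | 0.0300 | 0.913 |
| n = 35, at least 11 | 0.0364 | 0.929 |

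**The case against.** The strongest reply is that most of the text fixes or caps the evaluable number at 28. Section 17.2.3, the operating rule for stage 2, gives 28 as the evaluable total, and Sections 16.2 and 7.0 agree. The Protocol Revision History explains 35 as cover for screen failures and non-evaluable patients, with the goal still 28. On that view 35 is an enrolment ceiling. Under Section 16.3, moreover, evaluability is essentially known at first dose, so accrual could stop at exactly 28. These points stand, and they make a large overrun unlikely. They do not supply a rule for a small one, and Section 16.4 still calls 28 a minimum.

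A reader might infer two stronger things that the documents do not support.

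- **That the stated 5% level fails as soon as a 29th patient counts.** The written rule is 9 or more out of 28, with an observed DCR of at least 32%; it is not 9 out of however many are evaluable. Nine of 29 is 31.0%, which misses the stated rate. The error rate exceeds 5% only if the bare count is carried over, and the plan nowhere says that it will be.
- **That the false-positive risk is two to three times the nominal level.** Even with 9 carried over, the ratio at 29 to 31 patients is 0.0599/0.05 = 1.2 to 0.0839/0.05 = 1.7. It approaches 2 only at 32 (0.0972/0.05 = 1.9). The figure of 0.141 needs all 35 enrolled patients to be evaluable, contrary to the reason given for the extra places.

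**Conclusion.** The point holds as an internal contradiction that leaves the primary decision rule undefined above 28 evaluable patients. It is not an error in the sample-size calculation, which reproduces.

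The effect is conditional. With the count of 9 kept and stage 1 unchanged, one-sided type I error at 18% would be 0.060 to 0.084 over the plausible range of 29 to 31, against 0.0495 at 28. With the 32% rate kept, it would be 0.025 to 0.038 over the same range. The two readings can thus give opposite conclusions from the same data.

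This rests on three assumptions: accrual continues while the last scans are awaited, the Section 3.1.1 definition applies, and each extra evaluable patient has the same 18% chance of disease control under the null. It should be fixed before the final analysis, but it does not undermine the design.

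**What to change.** 1. Reconcile Sections 7.0, 16.2, 16.4 and 17.2.3, so that 35 is the enrolment ceiling and 28 is the number used for the primary decision.
2. Use one definition of evaluable for DCR, since Sections 3.1.1 and 16.3 differ.
3. State in Sections 16.2 and 16.4 that the primary decision uses the first 28 evaluable patients in order of first dose, the first 14 of them forming stage 1, and that any further patients are reported descriptively.

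This keeps type I error at 0.0495 and power at 0.905. It costs a few sentences and no additional patients.

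A printed table of cut-offs (10 for 29 to 32 patients, 11 for 33 to 35) would also hold the error below 5%. However, power would fall short of the stated 90% at 29 (0.862), 30 (0.888) and 33 (0.894), despite more patients being treated. The first-28 rule is preferable.
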